### 11.2.2 RPFNA specimen collection

All cells collected by the RPFNA procedures will be pooled into one tube containing 6 mL of Modified CytoLyt per the [Specimen Handling SOP](#). Briefly, the sample is labeled with participant ID, date of procedure, and sample type (RPFNA) and then capped and gently inverted 2-3 times to mix. The sample is placed on a test tube rocker at low speed (if test tube rocker is not available, then leave tube in wet ice). Within 24 hours, the sample must be shipped with the [RPFNA Cytology Sample Submission Form](#) via FedEx priority overnight service on a cold pack to the central processing lab at KUMC at the address below.

### 11.2.3 Processing the cytology sample at the central pathology lab:

Upon arrival to the KUMC central processing lab, one third of the CytoLyt suspended cellular sample will be processed for cytomorphology, and one third for evaluation of proliferative index and apoptotic index via Ki67 and caspase immunohistochemistry (IHC) staining, respectively. The remainder of the sample will be designated for tissue banking will be stored at -80C in RNAlater®. The cytomorphology sample will be processed first as outlined below, and that will be used to determine how the IHC slides will subsequently be prepared.

Cytomorphologic preparations are filtered through a 25-mm Millipore filter (5-m pore size) and cytocentrifuged, rather than smeared, to reduce cellular distortion and maximize cell yield per slide. If there are fewer than 10 cells on the cytomorphology slide, this will be noted in the pathology report, and the sample will be considered unevaluable for cytomorphology. The method for cytomorphologic assessment is described in Section 11.5.1.

Slides designated for IHC are sequentially fixed in 10% buffered formalin, methanol, and acetone. If there were fewer than 100 cells on the cytomorphology slide, the aliquots designated for Ki67 and caspase will be combined and used together for determination of proliferative index via IHC. In that case, the sample will be considered unavailable for apoptotic index. Proliferative index (and apoptotic index, when available) will be read as the number of cells with unequivocal nuclear staining per total number of ductal epithelial cells. If there were fewer than 500 cells on the slide, but more than 100, results will be considered evaluable but suboptimal. If there were fewer than 100 cells on the slide, that IHC measure will be considered unevaluable. Both of these IHC measures are described in detail in Sections 11.5.2 and 11.5.3, respectively.

RPFNA specimens processed in this manner typically result in slides with approximately 1000 epithelial cells per slide. Thus, we expect that cytomorphology, Ki67, and caspase, will be evaluable from nearly all breast epithelial specimens obtained by RPFNA.

### 11.3 **Blood collection and processing**

Peripheral blood will be sampled at baseline and annually while on treatment. For premenopausal participants, blood draws will be timed to occur during the follicular phase of the menstrual cycle (Days 2-10). All subjects will be asked to fast for at least 8 hours prior to blood draw.

Whole blood will be drawn into the following tubes:

- one 10 mL EDTA-containing lavender-top
- one 5 mL citrate-containing blue-top
- one 10 mL red -top vacutainer tube
- two 10 mL red tiger-top vacutainer SST tubes

All tubes are gently inverted 2-3 times after being drawn. Two of the red tiger-top tubes will require processing at the local site and should be placed on wet ice immediately after blood draw for transport to the specimen processing center. Specimen processing and handling are fully detailed in the [Specimen Handling SOP](#), and briefly discussed below.

#### 11.3.1 Processing and handling the K2EDTA-coated lavender-top tube

This tube should be inverted 8-10 times and then labeled with type of sample (whole blood), participant ID, and date of blood draw. Pre-printed cryogenic labels with the sample type will be provided. PLEASE WRITE IN THE PTID AND THE DATE OF THE SAMPLE WITH A FINE TIP SHARPIE PERMANENT MARKER. It will then be shipped ON DRY ICE ( $\geq 10$  pounds of dry ice) in the provided shipping container via FedEx priority overnight service (ship Monday thru Wednesday only), accompanied by the Blood and Urine Specimen Submission Form. If there is a delay between blood draw and shipment, the tube must be kept frozen at  $-80^{\circ}\text{C}$ . Do NOT store the blood at  $-20^{\circ}\text{C}$  for any length of time. This sample will be used for pharmacogenetic studies.

Address for site submission of blood and urine samples. The study coordinator will document the receipt of the samples and transfer to the coordinating center laboratory:

[name], MPH  
ATTN: LDtam study coordinator  
UAB Division of Peds Hem/Onc  
[name]  
[contact]  
Email: [[contact]](mailto:[contact])

#### 11.3.2 Handling the blue-top tube

The **blue-top tube** should be inverted 2-3 times to gently mix the blood in citrate and immediately transported to the CLIA-approved hematology laboratory at the local site for determination of anti-thrombin III (AT3) per institutional protocol. Results will be entered into a secure study website.

#### 11.3.3 Processing and handling the red-top tubes:

The **red-top tube** will be immediately transported to the CLIA-approved chemistry laboratory at the local site for determination of a fasting lipid profile per institutional protocols. Lipid profiles consist of triglycerides (TG), total cholesterol (TC), high-density lipoprotein (HDL), and low-density lipoprotein (LDL). Results will be entered into a secure study website.

**The two red tiger-top tubes** should be inverted five times immediately after blood draw to ensure mixing of clot activator with blood (do not shake vigorously). Label the tubes with participant ID and date of blood draw using a permanent marker. Tubes should be allowed to clot at room temperature, upright in a test tube rack for 30 minutes. The sera is then harvested by spinning in a balanced centrifuge at  $1200 \times g$  for 10 minutes. Sera is aliquoted into up to 10 study-labeled cryovials with 1 ml per aliquot and placed in a  $-80^{\circ}\text{C}$  freezer within 2 hours of collection time. All aliquots will be labeled with the provided cryogenic

labels (pre-printed with the aliquot number and sample type). PLEASE WRITE IN THE PTID AND THE DATE OF THE SAMPLE WITH A FINE TIP SHARPIE PERMANENT MARKER. Frozen serum samples should be shipped on DRY ICE ( $\geq 10$  pounds of dry ice) via FedEx priority overnight service (ship Monday thru Wednesday only) to the coordinating center using the provided shipping container, FedEx shipping label, and accompanied by the **Blood and Urine Specimen Submission Form**.

#### 11.3.4 Storage of blood samples

The whole blood and serum samples will be transferred to the UAB Institute for Cancer Outcomes and Survivorship laboratory, where they will be bar-coded, entered into a specimen tracking database, and stored at  $-80^{\circ}\text{C}$  until assays are performed.

### 11.4 **Urine collection and processing**

A spot urine sample will be collected at baseline and annually while on treatment. Two aliquots (3.5mL each) will be frozen at  $-20^{\circ}\text{C}$  and then shipped on dry ice as described in the **Specimen Handling SOP** to the address in Section 11.3.1, accompanied by a **Blood and Urine Specimen Submission Form**. This sample will be used for evaluation of N-telopeptides (NTX) as described in Section 11.8.2.

### 11.5 **Tissue-based biomarkers**

#### 11.5.1 Cytomorphologic scoring

*Cytomorphology* will be scored according to the Masood classification from epithelial cells retrieved via RPFNA. This scoring system assigns a score of 1 to 4 points to each of 6 morphologic characteristics: cellular arrangement, cellular pleomorphism, prevalence of myoepithelial cells, anisonucleosis, nucleoli, and chromatin clumping. A score of 6 to 10 is associated with nonproliferative specimens, 11 to 14 with hyperplasia without atypia, 15 to 18 with hyperplasia with atypia, and 19 to 24 with malignancy (Table 2) [99]. For cytology, intraobserver variance has been reported to range from 8-24% [100]. Slides will be hand scored by two readers. In the case of a difference between the two readers, the scores will be averaged. The first reading and second reading will be performed by KUMC-associated cytopathologists. De-identified stained slides will be sent to each reader for blinded review:

#### 11.5.2 Determination of tissue proliferative index

*Proliferative Index* will be determined using an immunohistochemistry (IHC) assay to evaluate Ki-67 expression from epithelial cells contained in RPFNA samples. A categorical estimate of the number of ductal epithelial cells present on the slides designated for proliferative index evaluation will first be assessed: less than 100, 100 to 500, 500 to 1,000; 1,000 to 5,000; or more than 5,000. Slides containing at least 100 epithelial cells will be processed for Ki-67 staining; if no slides meet this criterion, the subject will be deemed unevaluable for this endpoint at that time point. Antigen retrieval will be performed with 10 mmol/L citrate buffer (pH 6) and then will be stained with Ki67 clone MiB-1 monoclonal antibody (Dako North America, Carpinteria, CA) at a 1:20 dilution. Hyperplastic cell clusters will be preferentially assessed for nuclear staining. The number of cells with unequivocal nuclear staining out of 500 cells assessed will be recorded

as the proliferative index. Slides will be hand scored by two readers as described in Section 11.5.1, and in the case of a difference between the two readers, the scores will be averaged. Agreement between two readers using this method is excellent (Cronbach's  $\alpha = 0.99$ ; reported in [86]). Within-person reliability is also superb, with a previously reported intraobserver variance of 4% [100].

### 11.5.3 Determination of tissue apoptotic index

RPFNA cytology samples will be stored for future analysis of tissue apoptotic index. *Apoptotic index* will be determined using an IHC assay to evaluate cleaved caspase-3 expression from epithelial cells contained in RPFNA samples. After categorical estimation of the number of ductal epithelial cells present on the slides designated for apoptotic index, antigen retrieval will be performed as described above and slides stained with cleaved Caspase 3 rabbit polyclonal antibody (Cell Signaling Technologies, Boston, MA). The number of cells positively stained out of 100 will be recorded as the apoptotic index, with the subject deemed unevaluable for this endpoint if less than 100 cells are present on the slide. As above, slides will be scored by two readers as described in Section 11.5.1, and scores will be averaged if discrepant.

## 11.6 **Estrogen Assays**

Serum and RPFNA samples collected into saline will be stored at the coordinating center for future analysis of sex steroid hormone levels. At the time of analysis, the samples will be shipped to the Reproductive Endocrinology Research Laboratory of [name] at the University of Southern California. The methodology used is a radioimmunoassay (RIA) after a unique in-house extraction using column chromatography as outlined below. This technique is highly sensitive for monitoring circulating estrogens in postmenopausal women.

*Total Estradiol ( $E_2$ )* – One-tenth of a ml of serum is incubated with  $^3\text{H}$ - $E_2$  and extracted with hexane and ethyl acetate to remove unconjugated steroids. After evaporating under nitrogen, the residue is redissolved in isooctane and applied on a column of Celite impregnated with ethylene glycol.  $E_2$  is eluted in ethyl acetate in isooctane and redissolved in buffer. Then it is incubated with  $^{125}\text{I}$ - $E_2$  and anti- $E_2$  serum. Antibody-bound and unbound  $^{125}\text{I}$ - $E_2$  are separated by adding a second goat anti-rabbit antibody, centrifuging, and aspirating the supernatant. Total estradiol is then quantitated using a gamma counter.

*Bioavailable  $E_2$*  – is calculated by determining the *sex hormone binding globulin* (SHBG) level and subtracting that from the total estradiol level. SHBG is measured by a solid-phase, two-site chemiluminescent immunoassay using the Immulite analyzer. Alkaline phosphatase conjugated anti-SHBG polyclonal antibodies are introduced into the reaction tube, and the tube is incubated for 30 minutes at 37°C. SHBG in the sample is bound, forming an antibody sandwich complex. Unbound conjugate is then removed by a centrifuge wash, after which the chemiluminescent substrate is added, and the reaction tube is incubated for another 5 min. The chemiluminescent substrate undergoes hydrolysis in the presence of alkaline phosphatase, yielding an unstable intermediate. Continuous production of this intermediate results in the sustained emission of light. The light is measured by an illuminometer and is proportional to the concentration of SHBG in the sample

*Estrone (E1)* – is determined using 1 ml of serum, which is incubated with H-E1 and treated with the same extraction and column chromatography methods as with total estradiol but using I-E1 and anti-E1 serum with a second goat anti-rabbit antibody. Estrone is quantitated similarly after centrifugation and separation.

*Estrone Sulfate (E1S)* - One-third of a ml of plasma is incubated with H-E1S and is extracted with hexane and ethyl acetate, then deproteinized with methanol. After evaporating under nitrogen, the residue is reconstituted with sodium acetate buffer and hydrolyzed with arylsulfatase. The hexane:ethyl acetate extraction step is repeated, the extract is redissolved in buffer, and then the E1 RIA is carried out.

The assay sensitivities are as follows: E2 = 5 pg/ml = 1.36 pmol/L, E1 = 5 pg/ml = 1.35 pmol/L, and E1S = 0.16 ng/ml. Intra-assay and inter-assay coefficients of variation (CV) for all four assays are well below 15%, as tabulated below.

Assay	Intra-assay CV	Inter-assay CV
Total Estradiol	7.0%	9-13%
Sex Hormone Binding Globulin	4.1-7.7%	6-13%
Estrone	7.4%	8-10%
Estrone Sulfate	7.5%	11%

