## 1.0 OBJECTIVES

- 1.1 To determine the impact of a two-year course of low-dose tamoxifen administered at 5mg per day on surrogate endpoint biomarkers of breast cancer (BC) risk, including:
  - mammographic breast density (MBD), an established radiographic biomarker of BC risk,
  - cytomorphology and proliferative index, tissue biomarkers closely linked to BC risk, and
  - sex steroid hormones and insulin growth factors, circulating biomarkers of BC risk.
- 1.2 To establish safety and tolerability of this low-dose tamoxifen regimen, assessing both objective measures (lipid profiles, clotting factors and bone metabolism markers) and patient-reported outcomes.
- 1.3 To examine the modifying effect of demographic, clinical, and molecular characteristics on the risk: benefit ratio from this two-year low dose tamoxifen intervention.
- 1.4 To explore the relationship between this low-dose tamoxifen regimen and clinical measures of efficacy (new breast cancer and DCIS diagnoses) and toxicity (thromboembolic events, reports of hot flashes and gynecological symptoms, liver function abnormalities, and other cancer diagnoses).

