*Circulating biomarkers of BC risk* - Dose-response relationships have been noted between tamoxifen and multiple serum biomarkers of BC risk. These include decreased IGF-1 and increased IGFBP-3, as discussed earlier, as well as increased sex hormone-binding globulin (SHBG) levels [97, 98]. While these circulating biomarkers are correlated to BC risk, cytomorphology and proliferative Ki67 index are the only direct measures of breast tissue response to BC risk-reducing interventions. Sampling of normal breast epithelia to assess both biomarkers is feasible through a well tolerated method, RPFNA (please see discussion above). Nevertheless, this procedure is not considered standard of care for radiation exposed female CAYAC survivors, while annual screening mammography is. In addition, while MBD is evaluable on all digital mammograms, some RPFNA samples will not yield sufficient cells for Ki67 assessment. Therefore, we have chosen MBD to be the primary endpoint in the proposed chemoprevention trial.

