#### 11.11 **Pharmacokinetic and pharmacogenetic measures**

Plasma will be processed from each scheduled blood draw and will be stored for the measurement of tamoxifen levels and levels of the tamoxifen metabolites, N-desmethyl-tamoxifen (also known as endoxifen) and 4-OH-tamoxifen, at the time of trial completion.

Blood will be also processed for DNA to allow for analyses of P450 SNPs including CYP2D6 polymorphisms after trial completion and unblinding. Stored DNA may also be used to explore DNA adduct formation during the course of tamoxifen treatment.

The SNP studies will be performed using commercial assays developed by Roche Laboratories.

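### Bioavailable estradiol is defined in 11.6 as total estradiol minus the SHBG concentration, which is not a hormone level; the section's pmol/L sensitivities and the specimen for the plasma assays also need correcting

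*Combined protocol and SAP*

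**What the plan says.** Objective 1.1 names "sex steroid hormones and insulin growth factors, circulating biomarkers of BC risk" among the surrogate endpoints on which tamoxifen is to be assessed. Section 11.6 sets out the estrogen assays. Bioavailable estradiol is obtained by measuring SHBG and then: "SHBG) level and subtracting that from the total estradiol level". The SHBG method is a two-site immunoassay whose signal "is proportional to the concentration of SHBG in the sample". No albumin term, binding constant or unit is given. Section 2.4, under circulating biomarkers, lists "increased sex hormone-binding globulin (SHBG) levels" among the dose-related effects of tamoxifen.

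Section 11.6 also gives the assay sensitivities, "5 pg/ml = 1.36 pmol/L" for estradiol and "5 pg/ml = 1.35 pmol/L" for estrone. It runs estrone sulfate on plasma, although its opening sentence names serum as the blood specimen stored for the sex steroid assays. For tamoxifen and its metabolites, 11.11 says "Plasma will be processed from each scheduled blood draw". On central storage, 11.3.4 says only: "The whole blood and serum samples will be transferred".

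**The concern.** SHBG is a carrier protein, and its concentration is not an amount of estradiol. Subtracting it from total estradiol therefore does not leave the unbound or loosely bound hormone. The derived variable is dominated by SHBG with its sign reversed, and SHBG is something the study drug is expected to change. If the rule were followed, one marker in a class named in Objective 1.1 would have no interpretable size, and a between-arm comparison of it would largely restate the SHBG difference.

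Two further faults concern the same laboratory text. The pmol/L sensitivities do not follow from the pg/mL sensitivities. The specimen named for estrone sulfate and for the tamoxifen metabolites is one that the blood-handling section does not produce.

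**Working it through.** **1. Unit conversion.** The sensitivities are the plan's only printed figures here, and step 2 needs the same conversion. The molecular weights are physical constants that the documents do not give: estradiol (C18H24O2) 272.38 g/mol, estrone (C18H22O2) 270.37 g/mol.

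- The printed values are reproduced by multiplying: 5 × 272.38/1000 = 1.362 and 5 × 270.37/1000 = 1.352.
- The correct conversion divides: pmol/L = (pg/mL × 1000)/molecular weight. Estradiol: 5000/272.38 = 18.36. Estrone: 5000/270.37 = 18.49.
- The printed values are too low by 18.36/1.36 = 13.5-fold and 18.49/1.35 = 13.7-fold.
- Read as correct divisions, they would imply molecular weights of 5000/1.36 = 3,676 and 5000/1.35 = 3,704 g/mol.

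The match in the first line points to an inverted conversion, not a text-extraction fault. It casts no doubt on the 5 pg/mL limits.

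**2. Size of the subtraction.** The documents give no estradiol or SHBG levels. Assumed ranges: estradiol 5 to 400 pg/mL, SHBG 20 to 120 nmol/L.

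- Estradiol in nmol/L = (pg/mL)/272.38, so the range is 0.018 to 1.47 nmol/L.
- SHBG exceeds estradiol by between 20/1.4685 = 14-fold and 120/0.01836 = about 6,500-fold.
- Total estradiol minus SHBG, both in nmol/L, runs from 1.47 - 20 = -18.5 to 0.02 - 120 = -120. It is negative throughout.
- With units mixed (estradiol in pmol/L, SHBG in nmol/L), it runs from 18.4 - 120 = -102 to 1468.5 - 20 = 1,449. The sign then depends on the units chosen.

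**3. Effect on a treatment comparison.** Change in the derived value = change in total estradiol - change in SHBG.

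- With total estradiol unchanged, a 20% rise in SHBG (an assumed size) lowers the value by 0.2 × 20 = 4 to 0.2 × 120 = 24 nmol/L.
- A real fall in bioavailable estradiol cannot exceed the total present, at most 1.47 nmol/L on these assumptions. Even the smallest computed fall is larger than that.

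**4. Plasma.** Tubes listed in 11.3:

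| Tube | Handling | Section |
|---|---|---|
| EDTA | Frozen and shipped as whole blood for pharmacogenetics | 11.3.1 |
| Citrate | Sent to the local laboratory for antithrombin III | 11.3.2 |
| Red-top | Sent to the local laboratory for lipids | 11.3.3 |
| Two tiger-top | Serum, up to ten 1 mL vials | 11.3.3 |

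No tube is assigned to plasma, and 11.3.4 stores none. Section 11.6 (estrone sulfate) and 11.11 (tamoxifen and metabolites) both require it.

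**The case against.** The strongest objection is about consequence. Sex steroids are a future analysis under the study calendar footnote and 11.6. They are not among the biological response endpoints in 10.3, have no model in 12.4 and have no power calculation in 12.5. This stands, and it limits the importance of the point.

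A reader might infer that any tamoxifen effect seen on bioavailable estradiol would be purely an artefact. The documents do not support that. At a given total estradiol, a real rise in SHBG also tends to lower true bioavailable estradiol, so the direction could be right. The one-for-one fall also assumes that total estradiol does not change. Moreover, a same-unit subtraction that is negative throughout would probably be noticed. What survives is that the written rule gives a value of no valid size.

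A reader might also infer that results between 1.36 and 18.4 pmol/L would be wrongly treated as measurable. Nothing says results will be reported or censored in pmol/L, and the pg/mL limits are stated first.

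Finally, a reader might infer that no plasma can be had. EDTA and citrate tubes are drawn, 11.11 says plasma will be stored, and 11.3 defers full handling details to a Specimen Handling SOP that is not among the documents. The supportable statement is that the protocol sections disagree and must be reconciled.

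**Conclusion.** The definition of bioavailable estradiol is wrong as written and should be replaced before the assays are analyzed. That conclusion needs no assumed levels: 11.6 subtracts the concentration of a protein from that of a hormone. The illustrative sizes (about -18.5 to -120 nmol/L, and a 4 to 24 nmol/L fall for a 20% SHBG rise) do rest on the assumed ranges, and the fall also on unchanged total estradiol.

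The pmol/L sensitivities are in error by 13.5-fold (estradiol) and 13.7-fold (estrone), given the standard molecular weights. The plasma point is an internal inconsistency, not proof that specimens are missing. It reaches slightly further than the steroids, because 12.4 plans endoxifen at t1 and t2 as an exploratory effect modifier.

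Mammographic density, the sample size and the power are unaffected.

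**What to change.** - **Definition.** Calculate bioavailable estradiol from total estradiol, SHBG and albumin by a mass-action formula, with the formula, binding constants and units stated. Use one fixed albumin value for all participants: 9.1 does not list albumin in the metabolic panel, and using measured values only where available would mix two calculations. Report SHBG as a marker in its own right.
- **Sensitivities.** Change the pmol/L values to 18.4 (estradiol) and 18.5 (estrone), and leave 5 pg/mL as it is.
- **Specimen.** Reconcile 11.3 to 11.3.4 with 11.6 and 11.11. Name the stored serum as the specimen for estrone sulfate and tamoxifen metabolites if the laboratory confirms that it is acceptable. Spinning EDTA plasma before freezing would help future draws only; section 4.0 shows at least two years of accrual already past, and tubes already frozen as whole blood would not benefit.

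The cost is an edit to the laboratory section and one confirmation from the assay laboratory. No visit or blood draw is added. The limitation is that a fixed albumin value ignores differences between women in albumin, which should be acknowledged when the marker is reported.
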